During in vitro fertilization, human embryos are evaluated to assess their speed and morphological characteristics that allow prediction of their developmental potential and probability to achieve pregnancy and implantation. The advancement of the time-lapse technology enable us to understand the embryo development in vitro. IVF practices is improved by selection of the embryos with the highest implantation potential using time-lapse technology. Automated recording of embryos provides the opportunity to determine the exact timing of embryo cleavages and accurate selection of the viable embryos for transfer. EmbryoScope time-lapse system is the most used for IVF with over 300,000 patient treatments since 2009. The new time-lapse instrument, EmbryoScope+, is the newer model that provides the same result with 3.3 times greater capacity and a more efficient workflow with the automated registration of the EmbryoSlide+ culture dishes. It has been used in Scandinavia in over 500 treatments. We aim to compare the current EmbryoScope Time-Lapse System being used in IVF, which has become standard of care, to the new model EmbryoScope+ to demonstrate that the EmbryoScope+ is as safe and reliable as the EmbryoScope.

Brief study summary including, if applicable:

- Randomization arms: Standard EmbryoScope Time-Lapse system versus EmbryoScope+ on sibling oocytes.
- Length of time on treatment, length of follow-up: 10 months

Brief Summary:

- In-vitro Fertilization (IVF) will be completed according to normal clinical procedures. Participant's oocytes will be randomly assigned to one of two groups: Standard EmbryoScope versus EmbryoScope+.
- The best quality embryos are selected for embryo transfer and the pregnancy outcome is evaluated.
- Study participants will not be compensated.

Key eligibility:**Inclusion:**

40 years of age or younger (maternal)

65 years of age or younger (paternal)
Fresh or frozen (including donor) sperm can be used
Fresh or frozen oocytes (including donor), 10 or more oocytes
ICSI only
Frozen embryos from this study can be included in the outcome portion of this study.

Exclusion:

Patients with less than 10 oocytes
Co-culture patients

Study Design:

This is a randomized, controlled, single-center study in otherwise healthy infertile female subjects undergoing in vitro fertilization (IVF). The subjects recruited for this study will be among those patients who have been diagnosed with infertility and are planning to undergo IVF at the center where this study is being performed. The subjects will have undergone the usual informed consent procedure at the center.

Subjects will undergo ovarian stimulation, oocyte retrieval, IVF, and Intracytoplasmic Sperm Injection (ICSI) procedure following the center's usual procedures. At the time of retrieval, participant's oocytes will be randomly assigned to one of two groups: Standard EmbryoScope versus EmbryoScope+. The best quality embryos are selected for embryo transfer and the pregnancy outcome is evaluated.

"Best grade" embryos will be transferred regardless of EmbryoScope use. The standard EmbryoScope as well as the EmbryoScope+ monitor system as assigned during the randomization process will be used to observe the embryo development and document timing of embryo cleavages and morphology dynamics. Subjects will not be provided with the time-lapse images.

Endpoints will be Day 3 and Day 5/6 embryo development, implantation and pregnancy rate. The study is approximately 2 months, the estimated time it takes a physician to perform one IVF-ART treatment cycle. If embryos are frozen, the patient may be in the study until the time they choose to thaw the embryos or up to 1 year if they become pregnant. We aim to compare the current EmbryoScope Time-Lapse System being used in IVF which has become standard of care to the new model EmbryoScope+ to demonstrate that the EmbryoScope+ is as safe and reliable as the EmbryoScope.

Primary Objective:

Comparison of embryo development using standard assessments of morphokinetic parameters, embryo selection algorithms and standard embryo grading.

Secondary Objective:

- 1- Implantation and clinical pregnancy rates
- 2- Embryo transfer rate
- 3- Morphokinetic data
- 4- Frozen embryo transfer outcomes

Statistical Considerations:

The primary outcome of the study is the comparison of embryo development between oocytes assigned to Standard EmbryoScope versus oocytes assigned to EmbryoScope+. The proposed sample size is 100 subjects and their partner, if applicable. In order to compare embryo development (primary endpoint) and implantation rate (secondary endpoint), as well as resulting pregnancy outcome (secondary endpoint), between the two EmbryoScope devices, a sample size of 100 subjects (200 including partners) will result in approximately 1000 embryos available for randomization.

Each subject's oocytes will be randomly divided between the two study arms, resulting in at least 500 oocytes per study arm. With a sample size of 500 oocytes per study arm, a 95% confidence interval for the proportion of oocytes undergoing adequate embryo development (at day 3 and day 5/6) in each study arm can be constructed to be within $\pm 4.4\%$ of the observed proportion of oocytes experiencing adequate embryo development. This calculation assumes an adequate embryo development proportion of 50% to conservatively maximize the width of the obtained confidence intervals. The chi-square test or Fisher's exact test will be used, as appropriate, to compare the adequate embryo development proportion between the Standard EmbryoScope and EmbryoScope+ study arms. Similar analyses will be performed for the secondary endpoints of implantation proportion, pregnancy proportion, embryo transfer proportion, and descriptive morphokinetic data proportions. A univariate generalized estimating equations (GEE) model will also be used to compare the adequate embryo development proportion between the two study arms, correcting for clustering by subject (i.e., multiple oocytes per subject). Lack of any observed statistically significant differences between the two study arms will not constitute evidence of equivalence or non-inferiority between the two study arms; rather, estimates of the adequate embryo development proportion in each group will serve as preliminary data for further investigation (i.e., hypothesis-generating). All p-values will be two-sided with statistical significance evaluated at the 0.05 alpha level. Ninety-five percent confidence intervals for the adequate embryo development proportion, as well as the secondary outcome proportions of interest, will be calculated to assess the precision of the obtained estimates. All analyses will be performed in SAS Version 9.4 (SAS Institute, Inc., Cary, NC) and Stata Version 14.0 (StataCorp, College Station, TX). Note: The statistical considerations section was written in

conjunction with [name], in the Division of Biostatistics and Epidemiology, Department of Healthcare Policy & Research.

Pregnancy Rate will be defined as:

Biochemical pregnancy - positive beta hcg after embryo transfer

Clinical pregnancy - identification of fetal sac in ultra sound post embryo transfer

Ongoing pregnancy - identification of fetal heart in ultra sound post embryo transfer

Delivery rate - live birth

Miscarriage rate - positive fetal sac or fetal heart without live birth.

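### Implantation and pregnancy compared by device per transferred embryo are conditioned on selection by grade after randomisation, and can hide device effects that act through grade

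*Combined protocol and SAP*

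**What the plan says.** Under Study Design, each participant's oocytes are randomised at retrieval to the standard EmbryoScope or the EmbryoScope+. Transfer then ignores the assignment: best-grade "embryos will be transferred regardless of EmbryoScope use". The outcome is read after that choice: "The best quality embryos are selected for embryo transfer and the pregnancy outcome is evaluated". The Primary Objective lists standard embryo grading among the measures of embryo development.

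Statistical Considerations sizes the study to compare embryo development and also "implantation rate (secondary endpoint), as well as resulting pregnancy outcome (secondary endpoint), between the two EmbryoScope devices". The method is one sentence: "Similar analyses will be performed for the secondary endpoints of implantation proportion, pregnancy proportion, embryo transfer proportion, and descriptive morphokinetic data proportions". It follows the chi-square or Fisher test of the primary proportion. The GEE model that corrects for several oocytes per subject is named only for adequate embryo development.

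No denominator is given for implantation or pregnancy. Biochemical, clinical and ongoing pregnancy are each defined by a finding after embryo transfer. Key eligibility adds: "Frozen embryos from this study can be included in the outcome portion of this study". Frozen-transfer outcomes are a secondary objective.

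**The concern.** Randomisation makes the two sets of assigned oocytes comparable. It does not make the transferred embryos from the two devices comparable, because these were picked by grade from both devices' siblings in competition with one another. If one device lowers grade, fewer of its embryos are transferred, and those that are have passed the same contest as the other device's embryos. The loss then shows up in how many embryos each device supplies more than in how well each transferred embryo does.

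This is separate from the attribution problem when embryos from both devices are transferred together. It would remain if every transfer were a single embryo of known device.

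At stake are the implantation, clinical pregnancy and frozen-transfer comparisons. The protocol aims to show that the new device matches the old one in safety and reliability, and similar implantation rates are an obvious figure to cite for that. Nothing in the plan warns that the selection rule may have produced the similarity.

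**Working it through.** **The plan's own figure.** The only stated precision is ±4.4% for adequate development with 500 oocytes per arm at 50%: 1.96 × √(0.5 × 0.5 / 500) = 0.0438. It reproduces. It applies to assigned oocytes, before selection. The documents give no implantation rate and no precision for the secondary endpoints, so the values below are assumptions and only the pattern should be relied on.

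**Common set-up.** Five oocytes per device per subject (from the minimum of 10 in Key eligibility, split evenly), 300,000 simulated subjects, and a device loss of 0.5 SD unless stated.

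**Model 1: grade and true quality are the same.** Implantation logit = −2.2 + quality; the best of 10 is transferred.
- Average embryo: 13.3% vs 8.9%, a gap of 4.4 points.
- Best of 10 if the whole cohort were on one device: 35.0% vs 25.3%, a gap of 9.7 points.
- Per transferred embryo in this design: 31.8% vs 29.0%, a gap of 2.8 points.
- Lost against the whole-cohort contrast: 1 − 2.8/9.7 = 71%. Lost against the average embryo, in points: 1 − 2.8/4.4 = 36%. On the log-odds scale against the average embryo, about 70% is lost.
- With a 0.3 SD loss: 33.0% vs 31.2% per transferred embryo, against 35.0% vs 29.0% for the whole cohort; 1 − 1.8/6.0 = 70% lost.

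**Model 1 with imperfect grading.** The device lowers overall quality, and grade correlates with quality:

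| Grade–quality correlation | Per transferred embryo | Lost against whole-cohort contrast |
|---|---|---|
| 1.0 | 31.8% vs 29.0% | 71% |
| 0.7 | 25.8% vs 20.6% | 34% |
| 0.5 | 22.0% vs 16.3% | 17% |
| 0.3 | 18.4% vs 13.0% | 6% |

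The losses in the lower rows move by two or three percentage points between simulation runs. If the loss is in viability that grading does not see (correlation 0.5), the result is 22.6% vs 15.8%, and nothing is lost.

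**Model 2: the route of the effect is separated.** True viability V = ρ × (visible grade) + √(1 − ρ²) × (ungraded viability). An embryo implants if V exceeds the cut-off that gives 30% in an unaffected embryo. ρ runs from 0.3 to 0.9, with one or two embryos transferred. The share of the all-oocyte difference still present among transferred embryos, in points, is:
- effect on visible grade only: 28% to 43% (57% to 72% lost);
- effect on ungraded viability only: 104% to 154% (none lost);
- effect on both: 78% to 115%.

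Example at ρ = 0.5, one transferred, visible grade only: all oocytes 30.0% vs 21.9% (8.1 points); transferred embryos 57.0% vs 54.1% (2.9 points); 2.9/8.1 = 36% retained.

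**Where the missing difference goes.** With a 0.5 SD loss in grade, the better device supplies 70.3% of single transfers. Implantations per assigned oocyte multiply transfer share by the per-transfer rate. In Model 1 with perfect grading, 0.703 × 0.318 / 5 = 4.5% and 0.297 × 0.290 / 5 = 1.7%. That ratio (1.72/4.48 = 0.38) is more extreme than the ratio of average potential (8.9/13.3 = 0.67), because a better device also displaces the other's embryos from transfer.

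**Precision.** If 100 subjects each had one transfer, split evenly, and implantation were 40%, the 95% half-width for the per-transfer difference would be 1.96 × √(2 × 0.4 × 0.6 / 50) = 19 points. An attenuated difference would be hard to see.

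**The case against.** A reader might infer that selection removes most of any device difference, so that transferred embryos must look alike. The documents do not support this. They say nothing on how well grade predicts implantation, or on whether a device effect would be visible to grading. The 71% loss needs grade to equal true quality. With imperfect grading and a general loss of quality it falls to between 6% and 34%, and it vanishes for effects that grading misses. It also depends on the comparator: the same scenario loses 36% in points against the average embryo.

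Four further objections have weight.
- An effect acting through grade is what the primary endpoint measures, on all assigned oocytes before selection. The difference is not lost from the trial.
- The embryo transfer proportion is a listed secondary endpoint and would show a shift such as 70% to 30%. This stands, but the plan does not say to read implantation alongside it.
- Statistical Considerations states that non-significance is not evidence of equivalence or non-inferiority and calls the estimates hypothesis-generating. This limits the harm. It does not tell readers that the implantation estimates and their confidence intervals are conditional on selection.
- A per-transfer denominator is inferred. The plan refers to analyses similar to one based on assigned oocytes, so a per-oocyte reading is possible. The pregnancy definitions point the other way, and the gap itself needs closing.

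It is also tempting to say that frozen transfers make the problem worse. If the best embryos go first, the frozen pool is a remainder that reflects earlier choices, but no calculation here sizes that effect. Including frozen embryos also widens the transferred set beyond the first pick.

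**Conclusion.** The point holds for the secondary endpoints. Per transferred embryo, implantation and pregnancy by device are not compared between randomised groups, whatever the size of the resulting bias. This follows from the transfer rule and needs no simulation.

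The size depends on mechanism. For an effect acting only through visible grade, roughly half to three quarters is lost on most comparators and scales tried, and 36% on the mildest. The loss is smaller when grade predicts quality imperfectly and the device lowers quality overall. There is none when grading does not see the effect, and the difference may even be enlarged. These figures rest on assumed effect sizes, base rates and correlations. They show that the per-transfer comparison can hide a device effect, not that it will. The primary endpoint is not affected.

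**What to change.** In Statistical Considerations:

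1. State the denominator for implantation and for each pregnancy outcome.
2. Add implantations and live births per oocyte assigned to each device, with all assigned oocytes as denominator and fresh and frozen transfers counted cumulatively. Handle clustering by subject, for example by extending the GEE model already planned for the primary endpoint. Describe this as a test of device difference. It estimates neither an effect size nor the pregnancy rate of a patient whose whole cohort is cultured on one device.
3. Report it next to the embryo transfer proportion by device.
4. Keep implantation per transferred embryo as a descriptive figure, with fresh and frozen shown separately. Label it as conditional on best-of-both selection and not as evidence that the devices are alike.
5. Add a separate rule for attributing outcomes to a device when embryos from both are transferred together.

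The cost is a few sentences and one table from data the study already plans to collect. The downside is that per-oocyte rates are low (a few per cent in the illustrations) and competition for transfer inflates differences (ratio 0.38 against 0.67 above).

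### The ±4.4% per-arm precision treats 500 oocytes from 100 subjects as independent, and the planned per-arm 95% confidence intervals have no stated adjustment for clustering

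*Combined protocol and SAP*

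**What the plan says.** The combined protocol and SAP plans 100 subjects (Statistical Considerations). Eligibility requires at least 10 oocytes per subject (Key eligibility: "Fresh or frozen oocytes (including donor), 10 or more oocytes"). Each subject's oocytes are split at random between the two devices, "resulting in at least 500 oocytes per study arm".

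Four statements in Statistical Considerations bear on this point:

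- **Precision.** "With a sample size of 500 oocytes per study arm, a 95% confidence interval for the proportion of oocytes undergoing adequate embryo development" is given as within ±4.4% of the observed proportion. The section adds: "This calculation assumes an adequate embryo development proportion of 50% to conservatively maximize the width of the obtained confidence intervals".
- **Clustering.** "A univariate generalized estimating equations (GEE) model will also be used to compare the adequate embryo development proportion between the two study arms". This model is meant to allow for the fact that one woman contributes several oocytes.
- **Intervals.** "Ninety-five percent confidence intervals for the adequate embryo development proportion, as well as the secondary outcome proportions of interest, will be calculated". No method is named for them.
- **Use of the results.** The study disclaims any conclusion of equivalence or non-inferiority; instead, "estimates of the adequate embryo development proportion in each group will serve as preliminary data for further investigation".

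**The concern.** Oocytes from one woman tend to succeed or fail together, so 500 oocytes from 100 women usually carry less information about a proportion than 500 unrelated oocytes. The section acknowledges this when it compares the arms, but not when it states precision. The 50% assumption is conservative for the binomial variance only; it gives no protection against within-subject correlation.

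Two things are at stake. First, ±4.4% is the only figure offered in support of the sample size; there is no power calculation. Second, the per-arm estimates are the product the plan intends to hand on to later work. If their intervals are computed with the same independence formula, they will be too narrow and will overstate what is known.

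**Working it through.** **Inputs from the documents:** 100 subjects; 500 oocytes per arm; hence m = 500/100 = 5 oocytes per subject per arm; p = 50%; 95% confidence.

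**Input not in the documents:** the within-subject ICC. A range of 0.05 to 0.3 is assumed for illustration.

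**1. The plan's own figure.** 1.96 × √(0.5 × 0.5/500) = 0.0438, or ±4.4%. The stated number is reproduced with no design effect.

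**2. Allowing for clustering.** With equal numbers per subject, the variance of a per-arm proportion is multiplied by 1 + (m − 1) × ICC = 1 + 4 × ICC. So

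- half-width = 1.96 × √(0.25 × (1 + 4 × ICC)/500)
- effective n = 500/(1 + 4 × ICC)

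For example, at ICC 0.1: 1.96 × √(0.25 × 1.4/500) = 5.19%, and 500/1.4 = 357.

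**3. Coverage of an unadjusted interval.** A normal approximation is 2Φ(1.96/√(1 + 4 × ICC)) − 1. A beta-binomial simulation (100 subjects, 5 oocytes each, p = 50%, 40,000 runs per ICC) gives values about half a point lower, as expected with a discrete count.

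| ICC (assumed) | Design effect | Effective n | Half-width | Unadjusted coverage, approximation | Unadjusted coverage, simulated | Subject-clustered coverage, simulated |
|---|---|---|---|---|---|---|
| 0 | 1.0 | 500 | 4.38% | 95.0% | – | – |
| 0.05 | 1.2 | 417 | 4.80% | 92.6% | 92.1% | 94.6% |
| 0.1 | 1.4 | 357 | 5.19% | 90.2% | 89.7% | 94.7% |
| 0.2 | 1.8 | 278 | 5.88% | 85.6% | 85.1% | 94.7% |
| 0.3 | 2.2 | 227 | 6.50% | 81.4% | 80.7% | 94.8% |

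**4. When ±4.4% still holds.** Five per subject per arm is the minimum under an even split. With m per subject per arm, effective n = 100m/(1 + (m − 1) × ICC). At p = 50% this is at least 500 when ICC ≤ (m/5 − 1)/(m − 1):

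- m = 6: 0.2/5 = 0.040
- m = 8: 0.6/7 = 0.086
- m = 10: 1/9 = 0.111

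As m grows, effective n approaches 100/ICC from below. At ICC 0.2 that limit is 100/0.2 = 500, so at ICC 0.2 or above and p = 50% no number of oocytes from 100 subjects gives ±4.4%.

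A proportion far from 50% also helps. At p = 80%, ICC 0.1 and m = 5: 1.96 × √(0.16 × 1.4/500) = 4.1%.

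**5. The between-arm difference.** Splitting sibling oocytes makes this a within-subject comparison. If the ICC is the same within and across arms, its half-width is 1.96 × √(2 × 0.25 × (1 − ICC)/500): 6.0, 5.9, 5.5 and 5.2 points at ICC 0.05, 0.1, 0.2 and 0.3, against 6.2 under independence. Without that assumption the variance factor is 1 + 4 × ICC(within) − 5 × ICC(across), so the interval is narrower than under independence only if the across-arm ICC exceeds 0.8 times the within-arm ICC. With 0.2 within and 0.1 across, the factor is 1.3 and the half-width is 1.96 × √(0.001 × 1.3) = 7.1 points.

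**The case against.** The case on the other side has real content.

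- **The arithmetic is correct.** 4.38% does round to 4.4%. The fault is an unstated independence assumption, not a miscalculation. This stands as a description, but the assumption conflicts with the section's own recognition of clustering.
- **The primary outcome is the comparison, and the GEE covers it.** This stands, and it confines the point to the per-arm intervals.
- **The plan does not commit to a wrong interval.** The same GEE could supply cluster-robust per-arm proportions, so under-coverage is conditional on how the intervals are computed. This stands too. But the plan does not say the GEE will be used for them, and the only interval formula in evidence is the independence one.
- **The size depends on unfavourable inputs.** It uses p = 50%, the minimum oocyte count and an assumed ICC. At ICC 0.05 the change is only from 4.4% to 4.8%, and modestly larger yields would absorb it. Whether the loss is material therefore cannot be settled from the documents. Even so, p = 50% and 500 per arm are the plan's own inputs, and at those inputs any positive ICC makes the half-width larger than the one stated.
- **The study is hypothesis-generating.** No test or success criterion uses ±4.4%. That limits the harm, but estimates passed on as preliminary data need honest intervals.

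**Conclusion.** The concern holds. At the plan's stated inputs, ±4.4% is right only if oocytes from the same subject are uncorrelated. For an assumed ICC of 0.05 to 0.3 the per-arm half-width is 4.8% to 6.5%, and unadjusted 95% intervals would cover about 92% down to 81% of the time. These figures rest on the assumed ICC range, 5 oocytes per subject per arm, equal numbers per subject and a proportion of 50%. Higher oocyte yields or a proportion far from 50% soften the result, and at a small ICC can remove it. The trial is not invalidated and the planned between-arm GEE is unaffected. The plan should be corrected because its one precision claim is optimistic and its interval method is unspecified.

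**What to change.** Replace the precision sentence with, for example:

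> With 100 subjects, 5 oocytes per subject per arm and a proportion of 50%, the half-width of the per-arm 95% confidence interval is ±4.4% if oocytes are independent, and about ±4.8%, ±5.2%, ±5.9% and ±6.5% at a within-subject ICC of 0.05, 0.1, 0.2 and 0.3.

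Add:

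> Per-arm 95% confidence intervals for adequate embryo development will be taken from the GEE model with robust standard errors clustered on subject, and the estimated ICC will be reported.

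The same interval rule should cover any secondary proportion to which a subject contributes more than one oocyte or embryo, since the plan's interval sentence includes those outcomes.

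If precision for the between-arm difference is also quoted (about 6.0 down to 5.2 points over the same ICC range), state that it assumes a common ICC within and across arms, and that a lower across-arm ICC would widen it.

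The cost is two or three sentences, using a model already planned, with no change in enrolment. The only downside is a less favourable stated precision. The change should be made before analysis so that the interval method is prespecified.

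### The primary endpoint has two unranked analyses, the first ignoring clustering of sibling oocytes, and the ±4.4-point precision also treats oocytes as independent

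*Combined protocol and SAP*

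**What the plan says.** The design compares "Standard EmbryoScope Time-Lapse system versus EmbryoScope+ on sibling oocytes" (study summary, randomization arms). The Statistical Considerations section adds: "Each subject's oocytes will be randomly divided between the two study arms, resulting in at least 500 oocytes per study arm".

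That section then gives two analyses of one primary proportion. First, "The chi-square test or Fisher's exact test will be used, as appropriate, to compare the adequate embryo development proportion". Later, a univariate GEE model "will also be used to compare the adequate embryo development proportion between the two study arms, correcting for clustering by subject". No sentence ranks them or says what happens if they disagree at the two-sided 0.05 level set for all p-values.

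Between these two statements comes the rule for the other endpoints: "Similar analyses will be performed for the secondary endpoints of implantation proportion, pregnancy proportion, embryo transfer proportion, and descriptive morphokinetic data proportions". The GEE sentence that follows names only adequate embryo development.

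Precision is planned per arm: "With a sample size of 500 oocytes per study arm, a 95% confidence interval for the proportion of oocytes undergoing adequate embryo development" is put at ±4.4 points, assuming a proportion of 50%. The section promises 95% intervals for the primary and secondary proportions but gives no method for them. It also cautions: "Lack of any observed statistically significant differences between the two study arms will not constitute evidence of equivalence or non-inferiority".

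**The concern.** Oocytes from one subject share the same egg source and sperm source, so their outcomes are likely to be correlated. The authors recognised this, since they planned a model that corrects for it. The gap on the primary endpoint is that this model is not designated as the primary analysis. Two analyses of the same data can give different p-values, and the plan leaves the choice open until after the data are seen.

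For secondary endpoints counted per oocyte or per embryo, sentence order and wording suggest that no clustered analysis is planned at all.

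The per-arm precision figure is affected as well. The plan disclaims equivalence and presents its estimates as preliminary data for later work. The estimates and their intervals are therefore the main product, and an interval that is too narrow would mislead whoever designs the next study.

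**Working it through.** **Inputs.** From the documents: N = 100 subjects; at least 10 oocytes per subject (Key eligibility), hence m = 5 per subject per arm; Nm = 500 per arm; p = 0.5; two-sided 5% level. The documents give no ICC, so 0.1, 0.2 and 0.3 are assumed.

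**1. The plan's own figure.** 1.96 × √(0.5 × 0.5 / 500) = 0.0438, or ±4.4 points. It reproduces, but only with 500 independent oocytes per arm.

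**2. Per-arm precision with clustering.** The design effect is DE = 1 + (m − 1) × ICC = 1 + 4 × ICC. The half-width is 1.96 × √(0.25/500 × DE), and effective n is 500/DE. An independence-based interval covers 2Φ(1.96/√DE) − 1.

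| ICC | DE | Half-width (points) | Effective n | Coverage, formula | Coverage, simulated |
|---|---|---|---|---|---|
| 0 | 1.0 | ±4.4 | 500 | 95% | – |
| 0.1 | 1.4 | ±5.2 | 357 | 90.2% | 89.9% |
| 0.2 | 1.8 | ±5.9 | 278 | 85.6% | 84.6% |
| 0.3 | 2.2 | ±6.5 | 227 | 81.4% | 80.5% |

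**3. Between-arm test.** Let rw be the correlation between siblings in the same arm and rc the correlation between siblings in different arms. With an even split,

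Var(difference) = 2pq/(Nm) × f, where f = 1 + (m − 1)rw − m·rc.

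The chi-square test assumes f = 1, so its true size is 2[1 − Φ(1.96/√f)].

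- *Even split, rw = rc = ICC.* Here f = 1 − ICC = 0.9, 0.8, 0.7. Size is 3.9%, 2.8%, 1.9% (simulated 4.1%, 3.1%, 2.1%), so the test is conservative. The naive interval for the difference is 1.96 × √(2 × 0.25/500) = ±6.2 points. Multiplying by √f gives about ±5.9, ±5.5, ±5.2.
- *Each oocyte assigned independently* (arm count per subject binomial with 10 trials, probability 0.5). Simulated size is 5.1%, 5.2%, 5.0%, about nominal.
- *Even split, rw = 0.20, rc = 0.10 (assumed),* as might arise from a shared dish. Here f = 1 + 4 × 0.20 − 5 × 0.10 = 1.3. Size is 8.6% (simulated 9.1%), so the test is liberal.
- *Break-even.* f = 1 when rc = (m − 1)/m × rw = 0.8 × rw. Below that ratio the test is too liberal.

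A cluster-robust test gave 5.3% to 5.5% in all these settings. Simulations were beta-binomial, with 40,000 replicates per setting.

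**4. Can the two analyses disagree?** Yes. Under no true difference (even split, equal correlations), they fell on opposite sides of 0.05 in 1.6%, 2.2% and 3.4% of simulated trials at ICC 0.1, 0.2 and 0.3. For an illustrative true difference of 6 points at ICC 0.2, power by formula is 47% for chi-square and 56% for the clustered analysis.

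**5. Secondary endpoints.** This part rests on reading the text. The sentence on similar analyses follows the chi-square/Fisher sentence and precedes any mention of GEE, and the GEE sentence is confined to the primary proportion.

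**The case against.** The strongest reply is that the primary endpoint is largely handled: a suitable GEE is planned and only a label is missing. The study is declared hypothesis-generating, and no success claim in the Statistical Considerations section hangs on one p-value. With an even split, the arm proportions and their difference are the same under either method. This stands, and it limits the severity. It does not settle which standard errors and p-value are reported.

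The direction of error in the between-arm test is not established. With an even split and equal correlations the cost is lost power, not excess false positives, and the liberal case rests on assumed correlations. This also stands. It is a reason to prefer the clustered analysis, which stayed near 5% in every setting tried.

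The size of the effect depends on assumptions. At ICC 0.05 the half-width is ±4.8 points, coverage about 93% and chi-square size 4.4%. Ten oocytes is the eligibility minimum: at an assumed average of 15, the half-width at ICC 0.1 is ±4.6. With 10 oocytes, p = 0.3 and ICC 0.05, it is ±4.4. So the planned width may be roughly achieved in favourable cases. However, under-coverage of an independence-based interval gets worse with more oocytes per subject.

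The plan does not say the reported intervals will assume independence, so the under-coverage is conditional. Only the planning figure is shown to rest on that assumption. Finally, similar analyses could be meant to include the GEE. That is possible, and one sentence would settle it.

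**Conclusion.** The concern holds and should be fixed. The plan gives two analyses of one primary endpoint without ranking them, and the ±4.4-point figure is correct only for independent oocytes; both are clear from the text. At p = 0.5 with 500 oocytes per arm, any positive ICC makes that figure too small: about ±5.2 to ±6.5 points over an assumed ICC of 0.1 to 0.3 with five oocytes per subject per arm.

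The chi-square test may be conservative, nominal or liberal, depending on the allocation method and correlation structure, neither of which the documents specify. General inflation of false positives is not claimed. The secondary-endpoint part is the natural reading of the text, not a certainty. Among those endpoints, it concerns only outcomes counted per oocyte or per embryo.

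**What to change.** Replace the two unranked statements with wording such as:

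> The primary analysis of adequate embryo development is a binomial GEE with subject as the cluster, an exchangeable working correlation and robust standard errors. The proportion in each arm, their difference, the 95% confidence intervals and the p-value are taken from this model. Chi-square or Fisher's exact results are descriptive only. Secondary endpoints measured per oocyte or per embryo use the same clustered analysis.

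Two details need settling when this is written. State the link function and, if it is the logit, how the difference and its interval are derived. Say whether day 3 or day 5/6 development supplies the primary result. Restate the 4.4-point precision as a range over assumed ICC values.

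This rule should not be extended to per-subject outcomes such as pregnancy. Nor does it address the fact that best-grade "embryos will be transferred regardless of EmbryoScope use" (Study Design), which is a separate matter.

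The cost is wording and a little more analysis work; GEE is already planned in the named software. There are two downsides. Per-arm intervals become wider, about ±5.2 to ±6.5 points at ICC 0.1 to 0.3. Robust standard errors with 100 clusters run slightly above 5% (5.3% to 5.5% simulated).
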